#### **4. OBJECTIVE(S)/SPECIFIC AIMS AND HYPOTHESES**

- *A concise statement of the goal(s) of the current study.*
- *The rationale for and specific objectives of the study.*
- *The goals and the hypothesis to be tested should be stated.*

The specific aims of the study include:

-Eliciting and incorporating participant feedback in the development of required content and study procedures for implementation of a personalized, virtual

interventional trial to enhance low-intensity walking using behavioral change techniques

- Determine the feasibility of conducting a virtual, randomized control trial using participant selected behavioral change techniques
- Examine the novel individual-level heterogeneity of treatment effect made possible by the crossover, personalized trial design, and pool results across patients to efficiently estimate the overall efficacy of the four behavioral change techniques in increasing low-intensity walking by 2,000 steps, 5 days per week.
- Assess the relationship between individual behavior change techniques and walking self-efficacy.
- Elicit participant attitudes and opinions toward using Personalized Trials to help inform their personal wellness strategy

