## 8. NUMBER OF SUBJECTS

- *Indicate the total number of subjects to be accrued locally. If applicable, distinguish between the number of subjects who are expected to be pre-screened, enrolled (consent obtained), randomized and complete the research procedures.*
- *If your study includes different cohorts, include the total number of subjects in each cohort.*
- *If this is multisite study, include total number of subjects across all sites.*

We expect to pre-screen and enroll up to 180 potential participants in this study. Up to 60 participants will be recruited across the four preliminary (brief duration) phases. Up to 60 participants will be randomized to the 10 week personalized trial, first undergoing a 2 week baseline monitoring of their walking behavior, followed by 8 weeks of monitoring their walking in response to each of the four behavioral change techniques (2 weeks per technique).

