## 10. ENDPOINTS

- *Describe the primary and secondary study endpoints*
- *Describe any primary or secondary safety endpoints*

This study is a feasibility pilot whose primary objective is to assess the acceptability, scalability of implementation and participant satisfaction with a personalized trial methodology using behavior change techniques to promote low-intensity physical activity. Secondary endpoints include pooling personalized trial results to assess efficacy of BCTs utilized to promote walking behavior.

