## 12. STATISTICAL ANALYSIS

- *Describe how your data will be used to test the hypotheses.*
- *State clearly what variables will be tested and what statistical tests will be used.*
- *Include sample size calculations.*
- *If this is a pilot study, state which variables will be examined for hypothesis generation in later studies.*

The sample size of 60 participants for testing the Personalized Trial was chosen to have a sufficient number of participants to obtain a preliminary assessment of the feasibility of Personalized Trials of the four behavioral change techniques as

compared to baseline. The numbers of prompts and reports were based on expert recommendations and estimations about maximal duration of the trial to maintain patient engagement. Data will be reported transparently so that individual level heterogeneity can be assessed.

Means and standard deviations of step scores for baseline versus behavioral change strategy treatment period will be visualized using a column graph. The statistical significance of differences will be adjusted for time interval. The effects of treatment on number of steps will be assessed using generalized estimating equations (GEE) with an unstructured variance-covariance matrix for measures on the same day. This model accounts for possible autocorrelation and linear trends between steps across time.

Data from the four small sample preliminary phases will be considered as descriptive data/information and will not be statistically analyzed.

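### Section 12 names only BCT versus baseline, a non-randomised before-after comparison; the BCT-versus-BCT contrasts that random order protects are not named

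*Combined protocol and SAP*

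**What the plan says.** **Design.** Section 8 puts baseline first for everyone, with participants "first undergoing a 2 week baseline monitoring of their walking behavior, followed by 8 weeks" on the BCTs at two weeks each. Under Section 11 (Procedures), only participants with at least 80% adherence during baseline are randomised. Under Intervention Delivery, what is randomised is the order of the four BCTs over four two-week blocks. No prompt-free block sits among the four, and no washout is described. Section 11 also has the Fitbit mailed out for the baseline period, a daily baseline text that carries no activity prompt, and a description of each new BCT sent the day before its block starts.

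**Analysis.** Section 12 sets the BCTs against baseline: "Means and standard deviations of step scores for baseline versus behavioral change strategy treatment period will be visualized using a column graph". It continues: "The statistical significance of differences will be adjusted for time interval". It does not define the time interval. Treatment effects on steps are to be assessed by GEE, and "This model accounts for possible autocorrelation and linear trends between steps across time". No section names a pooled contrast of one BCT with another.

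**Aims.** The third aim in Section 4 concerns individual heterogeneity "made possible by the crossover, personalized trial design, and pool results across patients to efficiently estimate the overall efficacy" of the four BCTs "in increasing low-intensity walking by 2,000 steps, 5 days per week". Section 10 states: "Secondary endpoints include pooling personalized trial results to assess efficacy of BCTs utilized to promote walking behavior".

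**The concern.** The only comparison the analysis section names is one that the randomisation does not cover. Whatever changes between the first two weeks and the next eight, apart from the prompts, is part of BCT minus baseline: getting used to a new device, season, workload, habit. The linear trend removes this only if the change really is linear in study day. Any remaining bias is common to all four BCTs and does not shrink with more participants.

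The contrasts between BCTs are protected from common time trends by random order, yet they are not pre-specified. At stake is the pooled efficacy estimate that would be carried into later personalized trials.

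**Working it through.** **Inputs.** From Sections 8 and 11: baseline is days 1-14, the BCT blocks are days 15-70, and 14 + 4 × 14 = 70 days = 10 weeks, which agrees with Section 8. From Section 12: 60 participants, justified by feasibility alone. No power, SD or effect size is given, so there is no sample-size figure to reproduce. Curve shapes, the 1,000-step amplitude and the serial correlations below are assumptions.

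**1. Overlap of treatment with time.** Let *x* = 1 on BCT days and 0 in baseline.
- Sum of squares of *x*: 14 × 56 / 70 = 11.2.
- Sum of squares of day: 70 × (70² − 1) / 12 = 28,577.5.
- Mean day is 7.5 in baseline and 42.5 on BCT, a gap of 35, so the cross-product is 11.2 × 35 = 392.
- r² = 392² / (11.2 × 28,577.5) = 0.480, so r = 0.693.
- Variance inflation from the linear term = 1 / (1 − 0.480) = 1.92.

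This figure follows from the schedule if days are independent. Under assumed AR(1) correlation, with GLS weighting, it is 1.63 at 0.6 and 1.29 at 0.8.

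**2. If time interval meant period as a factor.** Five period columns and four BCT columns make nine. The four BCT columns add up to the same vector as the four intervention-period columns, so the rank is 8. BCT minus baseline is then not estimable, while BCT-versus-BCT still is.

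**3. Curved trend, true BCT effect zero (illustration).** The least-squares estimate is: linear-adjusted = raw difference − 35 × *b*, where *b* is the pooled slope within the two phases.

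Take a novelty effect 1000 × exp(−(day − 1)/τ) with τ = 7 days. The mean is 464 in baseline and 18 on BCT, so the raw difference is 18 − 464 = −446. With *b* = −2.4 per day, the adjusted value is −446 + 84 = −362.

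| τ (days) | Linear-adjusted bias, independence | Linear-adjusted bias, AR(1) 0.6 |
|---|---|---|
| 3 | −213 | −165 |
| 7 | −362 | −255 |
| 9 to 10 | about −379 | about −263 |
| 14 | −351 | −241 |
| 28 | −210 | −144 |

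The mirror shape, an early rise that levels off, gives the same sizes with a plus sign.

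**4. Effect that builds within each block (illustration).** Suppose that steps rise from 143 to 2,000 over the 14 days of each block and restart with the next. The true mean is 1,071. Under independence the unadjusted estimate is 1,071. Linear adjustment reads the within-block rise as trend (*b* = 8.75 per day) and gives 1,071 − 35 × 8.75 = 765.

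**5. BCT versus BCT.** With participant effects and a four-level period factor on intervention days, these contrasts have zero bias under any time trend common to all participants. This holds for the mean model without carry-over.

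Precision in daily SDs, with 60 participants, independence, balanced order and no missing days:
- One pair, same BCT effect in everyone: √(2 / (60 × 14)) = √0.00238 = 0.049.
- Average BCT minus baseline, linear-adjusted: √(1.92 × (1/(60 × 14) + 1/(60 × 56))) = √0.00286 = 0.054.
- If person-specific BCT effects are independent with an assumed SD of 0.5 daily SDs: pair √(0.00238 + 2 × 0.25/60) = 0.104; average minus baseline √(0.00286 + 0.25/(4 × 60)) = 0.062.

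**The case against.** This is a feasibility pilot. Efficacy is secondary, the sample size rests on feasibility, and no passage says that the comparison with baseline is randomised. Section 12 already plans a time adjustment. All of that stands, and it limits the point to the pooled efficacy estimate.

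The GEE with BCT as a factor could produce the BCT-versus-BCT contrasts. That is true as well: the gap is that they are not named, not that the model excludes them.

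A reader might infer that the baseline comparison cannot be estimated at all. That requires time interval to mean period as a factor. Section 12 does not say so, and its mention of linear trends makes continuous study time the likelier reading.

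A reader might also infer that Section 4 claims crossover-randomised evidence for overall efficacy. The sentence can be read that way, but the reference to the crossover may belong only to heterogeneity, with pooling as a separate clause.

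Two design features help in part. The daily baseline text partly matches message contact, though not time. The limit of 20 starters per day implies at least 60 / 20 = 3 start dates if 60 begin. Those could help separate calendar effects, but not time since receiving the device, and no such analysis is described.

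**Conclusion.** The point holds and should be addressed. BCT minus baseline is a non-randomised before-after estimate. Under the stated linear trend it is identified only by assuming linearity, at a variance cost of 1.92-fold under independence. These conclusions rest on the schedule alone, apart from the independence assumption behind the 1.92.

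The bias sizes (about −379 to −144 steps per day for decay constants of 3 to 28 days, under independence or AR(1) 0.6) rest on an assumed shape and amplitude and scale with the amplitude. A reader might infer that the plan overstates or understates efficacy by such an amount. The documents do not support this, because the mirror shape reverses the sign. Nor can one say that linear adjustment is always the better choice: it reduces the novelty bias at 7 days (−446 to −362) but moves the estimate away from the truth when effects build within blocks (1,071 to 765).

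**What to change.** 1. In Section 12, add the pooled within-participant BCT-versus-BCT contrasts on intervention days, with participant effects and a four-level period factor, as the randomisation-based comparison. State that they assume negligible carry-over. Add a sensitivity analysis that drops the first days of each block and also its last day, since the next BCT's description arrives the day before that BCT starts.
2. Keep BCT minus baseline for the 2,000-step question and label it a non-randomised before-after estimate. Define the time term as linear study day, report the estimate with its interval both unadjusted and linear-adjusted, and check sensitivity to excluding day 14, when the first description arrives.
3. State in the report that overall efficacy against no BCT rests on the before-after contrast.

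The cost is a few more model fits and some wording, with no new data or procedures. The claim of absolute efficacy becomes weaker. The added contrasts show which BCT does better, not whether walking rose. Their precision is similar to that of the linear-adjusted estimate only if BCT effects are the same in everyone; with differing effects they are less precise.

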## 9. STUDY TIMELINES

- *Describe the duration of an individuals participation in the study*
- *Describe the duration anticipated to enroll all study subjects*
- *The estimated date of study completion*

The initial phases of study participation will involve either a single session via a virtual interaction (electronic meeting, 1:1 interview or electronic correspondence) or remote evaluation of study message content and frequency over the course of five days. The last study phase will involve a total of 10 weeks of study participation: activity tracking using a Fitbit activity monitor for 10 weeks, and

responding to behavior change strategy prompts and surveys delivered via text message to a secure link for 8 weeks. At the end of the 10 week intervention period, a report containing the individual's responsiveness to each BCT will be sent to the participant, along with a satisfaction survey.

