In the four preliminary phases (with up to 10 participants each in phase 1,3, 4 and up to 30 participants in Phase 2), virtual focus groups and/or 1:1 discussions will be held to answer questions and elicit feedback about the comprehensibility of behavior change strategy descriptions, special study website content and videos, the ability to receive “sample” study messages in home and work settings, the virtual informed consent process, and study tools with attention toward for clarity and ease of use.

Potential participants for the Personalized Trial Participants will be sent a secure message with the start date of their baseline period, as well as a review of what to expect during onboarding to the study. They will be mailed an initial study kit including a Fitbit device. A PDF copy of their electronically signed consent form will be made available to all participants via N1Thrive/REDCap secure messaging. Potential participants will be asked to download the Fitbit app to their smart phone. No more than 20 participants will be permitted to begin on the same day.

The baseline period will take place over the course of two weeks. During the baseline period, potential participants will be asked to wear their Fitbit for 10 ours per day and also while they are sleeping, as tolerated and to acknowledge receipt of a daily text message that is not an activity prompt. Baseline participants will be instructed to sync their Fitbit device by opening the Fitbit app on their phone at least every two days.

Individual adherence to Fitbit wear and to survey responses will be assessed in order to determine which individuals progress to intervention. Adherence to Fitbit wear will be defined as recorded activity of greater than 10 hours a day. Text message adherence will be defined as responding to a given text message. Baseline participants that do not achieve at least 80% adherence of Fitbit wear and text responsiveness the baseline period will be withdrawn from the study. Those that maintain at least 80% adherence will be randomized to one of their selected behavior change techniques to begin their pilot personalized trial. Participants who are randomized to receive intervention sequences will receive email confirmation including their protocol timeline. Enrollment will continue until up to 60 participants have been randomized.

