#### Intervention Delivery

This pilot study will use text messages to deliver four behavioral change techniques identified in Michie et al.’s (2011) paper which identified those BCTs associated with influencing change in physical activity behavior. These BCTs were updated to align with current BCT definitions using Michie et al.’s (2013) Taxonomy of Behavioral Change Techniques. A list of BCTs is provided as an appendix to this protocol. Participants will also receive **bi-weekly surveys** to assess their satisfaction with the given BCT and walking self-efficacy. BCTs will be provided to participants in a randomized crossover design with each BCT delivered individually in one of four 2-week blocks. The order in which participants receive BCTs will be randomized with the randomization order determined by the study

statistician. Prior to BCT delivery (i.e. every two weeks) participants will be sent information/BCT descriptions the day before they start their new BCT so that they understand the differences between the four BCTs for their personalized trial. For instance, BCT descriptions may include:

BCT Name	Definition	Sample Text Message Prompt
Goal Setting Behavior	Set or agree on a goal defined in terms of behavior to be achieved	Set the goal of being more active today. Record your goal
Action Planning	Prompt detailed planning of performance of behavior (must include a setting frequency, duration, and intensity)	“It’s Tuesday. Walk 2,000 steps from 10am -11am this morning.”
Self-Monitoring of Behavior	Establish a method for person to monitor and record their number of active periods based on their Fitbit	“It’s time to check your FitBit dashboard and view how active you have been today.”
Feedback on Behavior	Monitor and provide informative or evaluative feedback on performance of the behavior (e.g. form, frequency, duration, intensity)	“You met your goal yesterday. You walked 2,000 steps more than baseline.”

Participants may receive additional text messages to those outlined above with important reminders to sync their data as needed.

Upon completion, participants in the personalized trials phase will receive an individual report that demonstrates their walking responses in relation to their assigned BCTs and a satisfaction survey to obtain feedback about their personalized trials experience.

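### The step model has no day-of-week term, so uneven loss of weekend days can shift a block mean, mainly in baseline comparisons and individual reports; the effect is modest and the fix is one covariate.

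*Combined protocol and SAP*

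**What the plan says.** Section 12 gives the whole step analysis in a few lines. Steps are modelled by "generalized estimating equations (GEE) with an unstructured variance-covariance matrix for measures on the same day". It adds that "The statistical significance of differences will be adjusted for time interval", without defining the interval, and then that "This model accounts for possible autocorrelation and linear trends between steps across time". There is no covariate list, and no section mentions day of week, weekends or a weekly cycle.

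The design fixes the block lengths. Section 11 states "The baseline period will take place over the course of two weeks", and under Intervention Delivery has "each BCT delivered individually in one of four 2-week blocks", where BCT means behaviour change technique. BCT order is randomised; baseline always comes first.

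On missing days, section 11 says "Adherence to Fitbit wear will be defined as recorded activity of greater than 10 hours a day" and sets a gate for progression: "Those that maintain at least 80% adherence will be randomized". For the intervention blocks, section 16 gives no numeric wear limit; the principal investigator decides on continued eligibility after repeated deviations. No section says whether days with too little wear are excluded from the step analysis.

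Section 9 promises each person a report whose "responsiveness to each BCT will be sent to the participant". The statistical method behind that report is not described.

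**The concern.** All participants are employees, and the walking goal is itself framed by the week (2,000 extra steps on five days). Weekday and weekend step counts may well differ. A linear trend cannot follow a seven-day cycle. Autocorrelation describes how days co-vary; it does not correct a mean that has moved because certain days were not observed.

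Balance of weekdays across blocks therefore rests on the calendar alone, and holds only while the weekday mix of observed days is the same in each block. If a participant tends to leave the device off at weekends in one block and not in another, the difference between those blocks includes part of the weekday-weekend gap.

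Two uses of the data have least protection. The comparison with baseline, which section 12 names, is not randomised, and baseline carries a wear gate that later blocks lack. In a single person's report, an imbalance cannot average out over participants.

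**Working it through.** The documents state no figure on this point, so there is none to reproduce. The weekday-weekend gap D, the residual day SD and the autocorrelation are not given; the values below are assumptions shown over a range.

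**Inputs from the plan.** Each block has 14 days, hence 4 weekend days and 10 weekdays, whatever day it starts. The 80% gate requires 0.8 x 14 = 11.2, so 12 wear days pass (12/14 = 85.7%) and 11 do not (11/14 = 78.6%): up to 2 days may be lost at baseline.

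**Complete data.** Every block has the same weekend share, 4/14, so the cycle cancels from every difference between blocks. What remains is residual variance of D² x (10/14) x (4/14). Removing it lowers the model-based SE by 1 - sqrt(SD² / (SD² + 0.204 D²)):

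| D (steps) | SD 2,500 | SD 3,500 |
|---|---|---|
| 1,000 | 1.6% | 0.8% |
| 2,000 | 6.0% | 3.2% |
| 3,000 | 12.1% | 6.7% |

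A simulation of one person over 70 days (SD 3,000, AR(1) 0.2, D = 2,000, no missing days) agrees. The BCT-minus-baseline estimate had the same mean and the same sampling SD (1,308) with and without the weekend term, while the average model-based SE went from 1,155 to 1,101. Both lie below 1,308 because the least-squares fit ignored the autocorrelation. The SE statement therefore presumes that autocorrelation is handled, as the plan says it will be.

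**Two days lost, both on a weekend.** The weekend share falls from 4/14 to 2/12, so the block mean shifts by D x (4/14 - 2/12) = 0.119 D: 119, 238 or 357 steps/day for D = 1,000, 2,000 or 3,000. The goal averaged over a week is 2,000 x 5/7 = 1,429 steps/day, or 2,000 if walked every day, since section 6 says five to seven days. The shift is thus 6% (119/2,000) to 25% (357/1,429) of the goal. This is the extreme for a two-day loss.

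**Two days lost at random.** The number of weekend days lost is hypergeometric with variance 2 x (4/14) x (10/14) x (12/13) = 0.377 and SD 0.614. The weekend share then has SD 0.614/12 = 0.051, centred on 4/14. The shift averages zero with SD 0.051 D: about 51, 102 or 153 steps. At D = 2,000 a two-block contrast in one person has SD 102 x sqrt(2) = about 145, and the average over 60 people 145/sqrt(60) = about 19.

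**Effect of the unequal wear gate.** The same simulation was run with at least 12 baseline days required and no limit later. Assuming 30% of weekend days and 5% of weekdays lost, the mean BCT-minus-baseline contrast with and without the weekend term differed by 20, 33 and 57 steps at D = 1,000, 2,000 and 3,000. With 50% of weekend days lost, the differences were 50, 97 and 140.

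**The case against.** The strongest reply is that two-week blocks already solve the problem. For complete data that is correct. A reader might infer that individual estimates carry extra noise from the weekly cycle even then; they do not, because the cycle cancels and only the reported SE is affected. Even that matters only if the individual report uses a model with an SE, which the documents do not say.

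A reader might also take 119-357 steps as a bias in the pooled BCT results. That would need every participant to lose two weekend days in one block and none in the comparator. Order is randomised, so weekend loss unrelated to the BCT averages out of pooled BCT-versus-BCT contrasts, and nothing in the documents suggests that loss depends on the BCT. In one person, random loss is also minor: against a simulated SE of about 1,160, a shift SD of 145 adds (145/1,160)² = 1.6% to the variance.

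Further, the 80% rule is a gate for progression, not a stated analysis exclusion. If under-worn days are kept with low counts, the error comes from non-wear and a weekend term does not correct it. Staff may also work shifts, so a calendar weekend may capture their cycle poorly. Finally, section 10 makes acceptability, scalability and satisfaction the primary objective; step efficacy is secondary.

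All of this stands, and it limits the size of the point. It does not remove the exposure of the baseline comparison and the individual reports. The undefined time interval does not help either: nothing ties it to day of week.

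**Conclusion.** The omission is real and of minor weight. With complete blocks, or with the same weekday mix lost in every block, the estimates are sound and only the model-based SE of a single-participant analysis is overstated. A weekend term would lower that SE by about 1-12% over the assumed gaps and SDs.

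With uneven loss, and if inadequately worn days are absent from the analysis, one block's mean can move by up to 0.119 of the gap when two days are lost, and typically by about 0.051 of it when the loss is random. The comparisons at risk are BCT versus baseline and the individual reports. The documents do not support a claim that pooled BCT-versus-BCT contrasts are biased. The size and direction of any gap, and the pattern of loss, are assumptions throughout.

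**What to change.** Name calendar day of week (6 degrees of freedom) or a weekend indicator (1 degree of freedom) as a covariate in the section 12 GEE and in any model used for the individual reports. It is derived from the date of each daily step count, so it needs no new data.

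A workday/non-workday flag is not a free alternative: no section lists work schedules among the data collected, and they cannot be read from the date.

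State beside the new term that it addresses the mix of observed days only. It does not repair under-counted days that stay in the analysis, so the section should also say whether such days are kept or dropped.
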